4.1.2 Times used in the Primary and Secondary Outcome Definitions

For Cohorts 1-3 and 10-11 (Arms A and C) evaluations will occur on the infusion day (Day 0) prior to the infusion and at hours 0, 2, 4, 6, and 10 (\pm 15 min) post infusion. Additional follow-up will occur at Day 1 (\pm 4 hrs), 2 (\pm 8 hrs), and 3 (\pm 12 hrs) and at Weeks 1 (\pm 1 day), 2 (\pm 2 days), 4 (\pm 2 days), 8 (\pm 7 days), 12 (\pm 7 days), and 24 (\pm 7 days).

For Cohorts 5-8 (Arm B) evaluations will occur on the infusion day (Day 0) prior to the infusion and at hours 0, 2, 4, 6, and 10 (\pm 15 min) post infusion. Additional follow-up will occur at Day 1 (\pm 4 hrs), 2 (\pm 8 hrs), 3 (\pm 12 hrs), 4 (\pm 12 hrs), 7 (\pm 1 day), and 10 (\pm 1 day) and at Weeks 2 (\pm 2 days), 3 (\pm 2 days), 4 (\pm 2 days), 8 (\pm 7 days), 12 (\pm 7 days), and 24 (\pm 7 days).

For Cohort 4 (Arm A), evaluations will occur on the first infusion day (Day R) prior to the infusion and at hours 0, 2, 4, 6, and 10 (\pm 15 min) post-infusion. Additional first infusion follow-up will occur at Day 1 (\pm 4 hrs), 2 (\pm 8 hrs), and 3 (\pm 12 hrs) and Weeks 1 (\pm 1 day), 2 (\pm 2 days), 4 (\pm 2 days), and 10 (\pm 7 days). The R + Wk 10 visit may be repeated if the subsequent infusion is delayed.

For the second and third infusions, evaluations will occur on the infusion day (Day R) prior to the infusion only. Additional second and third infusion follow-up will occur at Day 2 (as indicated) and Weeks 1 (\pm 1 day), 2 (\pm 2 days), 4 weeks (\pm 2 days), and 10 weeks (\pm 7 days). All of these firsts are relative to the last infusion, Day R. Again, the R + Wk 10 visit may be repeated if the subsequent infusion is delayed.

Per Protocol Version 2.0 CM #2 (March 24, 2020), Cohort 4 participants with infusion interruptions caused by the COVID-19 pandemic were referred to the Arm A, single dose SOE (Table 6.1-1) and thus may have additional visits at R + Week 12 (\pm 7 days) and R + Week 24 (\pm 7 days).

For the fourth, and final infusion, evaluations will occur on the infusion day (Day R) prior to the infusion and at hours 0, 2, 4, 6, and 10 (\pm 15 min) post-infusion. Additional fourth infusion follow-up will occur at Day 1 (\pm 4 hrs) and 2 (\pm 8 hrs), and Weeks 1 (\pm 1 day), 2 (\pm 2 days), 4 (\pm 2 days), 12 (\pm 7 days), 24 (\pm 7 days), and 36 (\pm 7 days).

The protocol windows described above will be expanded to create 'analysis windows. These analysis windows will be defined as non-overlapping intervals spanning approximately the entire period of follow-up, starting and ending halfway between each successive study visit for which a specified evaluation is expected. This decision was made to increase data availability at later follow-up time points with minimal impact to study results. If there are multiple evaluations within the window for a given visit, the evaluation closest to the definition of scheduled study week will be used.

4.2 Analysis Approaches

4.2.1 Analysis of Primary Objectives

Safety and tolerability

All Grade ≥ 3 AEs that are **at least possibly** related to study treatment (as judged by the core safety team, blinded to study treatment) any time from study treatment administration through the entire follow-up will be summarized. The primary safety outcome will be summarized as the percentage of participants experiencing the above defined AE with 2-sided 95% confidence interval using exact binomial methods, separately for the active treatment group of each cohort and for the combined placebo groups (Arms A and C only). All data gathered for Cohort 4 participants will be used when pooling placebo participants. The analysis will use the Safety population defined in section 4.1.1.

Details of each AE included as the primary safety outcome will be provided in listings: cohort, study treatment, event description, grade, lab value and units, days of event post first infusion, days of event post most recent infusion (Cohort 4 only), date of onset, date of resolution, and relationship to study treatment (as judged by the core safety team).

Similar listings will be provided for SAEs and AEs, regardless of grade, that were related to study treatment or procedure (as judged by the core safety team). In addition, all AEs reported any time from study treatment administration through the entire follow-up will be summarized for the active treatment group of each cohort and for the combined placebo groups (Arms A and C only).

Pharmacokinetics

AUC_{12WK} for all cohorts will be summarized for the active treatment group by cohort in the PK population. The method for AUC estimation will be outlined in a separate PK plan. **Due to the limited sample size in Arm B, the pre-planned analyses using a linear regression model to estimate the mean difference between same dose cohorts in arm A vs. arm B is not feasible. AUC_{12WK} will be estimated for participants with sufficient data. For arm B participants, only descriptive statistics will be provided. The geometric mean ratio (and corresponding**

confidence interval) of dose-normalized AUC_{12Wk} (natural log transformed) will be estimated for Arm A vs. Arm C.

Sensitivity analysis including the active treatment subset of the Safety population as defined in Section 4.1.1 will be conducted.

Efficacy

For the primary efficacy analyses for Arm B cohorts, reduction in plasma HIV-1 RNA (\log_{10} copies/mL) from baseline to Day 7 will be summarized, both in a combined cohort and in each cohort separately. The comparison between pre- and post-treatment will be carried out using a paired t-test with 2-sided 95% confidence interval for the combined cohort, and a Wilcoxon signed rank test for each cohort separately. The analyses will use the Efficacy population defined in Section 4.1.1. **Sensitivity analysis will be carried out using a Wilcoxon signed rank test for the combined cohort.**

Sensitivity analysis including the Safety population as defined in Section 4.1.1 will be conducted.

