2.2 Regimen

Double-blind randomization in Arms A and C will be 2:1 SAR441236:placebo. Arm B participants will all receive open-label SAR441236.

Arm A (Treated, virologically suppressed)

- Cohort 1: 1 mg/kg of SAR441236 or saline placebo administered as a single intravenous (IV) infusion. Cohort 1 enrollment was completed under Protocol Version 2.0.
- Cohort 2: 3 mg/kg of SAR441236 or saline placebo administered as a single IV infusion. Cohort 2 enrollment was completed under Protocol Version 2.0.
- Cohort 3: 10 mg/kg of SAR441236 or saline placebo administered as a single IV infusion. Cohort 3 enrollment **was completed** under Protocol Version 2.0.
- Cohort 4: 30 mg/kg of SAR441236 or saline placebo administered as an IV infusion every 12 weeks for a total of four infusions. Cohort 4 enrollment **began** under Protocol Version 2.0 **and completed under Protocol Version 3.0**.

Arm B (HIV viremic)

- Cohort 5: 1 mg/kg of SAR441236 administered as a single IV infusion. **Cohort 5 enrollment began under Protocol Version 2.0 and was closed with Protocol Version 3.0.**
- Cohort 7: 10 mg/kg of SAR441236 administered as a single IV infusion. **Cohort 7 never opened to enrollment.**
- Cohort 8: 30 mg/kg of SAR441236 administered as a single IV infusion. **Cohort 8 enrollment began under Protocol Version 3.0. No additional participants enrolled under Protocol Version 4.0.**

In protocol Version 4.0, participants in Arm B will initiate or re-initiate combination non-study-provided ART on Day 14.

Arm C (ART-treated, virologically suppressed)

- Cohort 10: 0.3 mg/kg of SAR441236 or saline placebo administered once via a single subcutaneous (SC) injection on a single day.
- Cohort 11: 1 mg/kg of SAR441236 or saline placebo administered once via single or multiple SC injections on a single day.

Figure 1: Schema Arm A

[figure not shown]

Figure 2: Schema Arm B

[figure not shown]
[figure not shown]

Figure 3. Schema Arm C

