2.5 Overview of Sample Size Considerations

The total sample size of this study is **53-65** evaluable participants (**39-51** active-treated participants and 14 placebo participants). In Arms A and C, the proposed sample size provides a reasonably high probability of dose escalation when the true event rates are in fact acceptable, as well as providing low probability of dose escalation when the true event rates are unacceptable. In Arm B, the proposed sample sizes and dose de-escalation scheme (described in Protocol Section 10.4.2) provide a reasonably high probability of dose de-escalation when the true response rate (i.e., HIV-1 RNA reduction of at least $1.0 \log_{10}$ copies/mL from baseline by Day 14) for a given dose cohort is high.

For the primary outcome measure of efficacy in Arm B, the study has 80% power to detect a drop of $1.7 \log_{10}$ copies/mL in plasma HIV-1 RNA in each cohort with $N = 6$.

In all cohorts, participants who do not receive study treatment or who receive less than 90% of their first or only intended infusion or SC injection dose will be replaced. Arm A or Arm C participants who discontinue the study prior to Day 14 without having met the primary safety endpoint **OR. Beginning with Version 4.0 of the protocol, have an entry plasma HIV-1 RNA <5000 copies/mL**, will be replaced to ensure enough **efficacy** data are available for dose **de**-escalation evaluation. The CST may decide on additional replacements if primary endpoints cannot be adequately assessed due to missing data or incorrect infusion procedure. Participants who initiate the infusion or SC injection but receive less than 90% of their first or only intended dose will be encouraged to remain on study and complete all study follow-up.

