4.2.2 Analysis of Secondary Outcomes

- **Plasma HIV-1 RNA (\log_{10} copies/mL) at baseline and post-infusion for treatment-naïve, viremic participants with HIV (Arm B cohorts)**

Longitudinal participant-specific plots for antiviral activity before initiation of ART will be presented for each participant in Arm B. **Given the little evidence of viral decay in Cohort 5 and the limited sample size in Cohort 8 (n=2), the planned modelling for viral decay will not be conducted.**

- **Change in plasma HIV-1 RNA (\log_{10} copies/mL) from baseline (defined as the last measurement taken prior to treatment initiation) to Day 7 and Day 14 of monotherapy, and maximum reduction during 14 days of monotherapy for treatment-naïve, viremic participants with HIV (Arm B cohorts)**

Similar analyses described in section 4.2.1 for the primary efficacy endpoint at Day 7 will be conducted for the Day 14 results. Summary statistics will be provided for the maximum reduction of each participant by dose cohort during monotherapy of SAR441236 (post-infusion and before ART initiation). **Protocol Version 4.0 considers the maximum reduction during 14 days of monotherapy because the timing for ART initiation/re-initiation was changed from “by 28 days” (Version 3.0 or earlier) to “at 14 days” for Arm B participants. However, since no participants enrolled under Version 4.0, we consider maximum reduction occurring in up to 28 days of monotherapy for Arm B participants.**

- **Attributions of anti-SAR441236 antibodies in all cohorts.**

The ADA status of participants exposed to anti-SAR441236 antibodies will be tabulated by scheduled visit day/week. Details of participants who developed anti-SAR441236 antibodies will be provided.

- **Change in CD4⁺ T-cell counts (cells/mm³) from baseline to week 12 following single dose of SAR441236 for all cohorts and the change in CD4⁺ T-cell counts (cells/mm³) from baseline to week 12 following each infusion for Cohort 4.**

Longitudinal participant-specific plots and numerical summaries for change from baseline in CD4⁺ T-cell counts (cells/mm³) will be presented by cohort.

- **Pharmacokinetic parameters of SAR441236 following each infusion.**

Descriptive numerical summaries of the following PK parameters (protocol section 11.3) by dose cohort will be presented:

Single dose:

- Maximum concentration (C_{max})
- Time of maximum concentration (T_{max})
- Dose-normalized maximum concentration
- Terminal half-life

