- Analysis windows have been widened to capture as much information as possible. For participants who received their infusion shortly before the pause, they were directed to the Single Dose Arm A SOE (Table 6.1-1 in Protocol Version 2.0) after they had reached Week 4 to reduce site burden. This will cause slight differences in visit schedules across Cohort 4 participants. However, the majority of these were virtual (no lab data collected) so the need to align lab results (e.g., CD4+ T-cell counts) will be negligible.

Arm B Single Dose Cohort (5) Considerations

- Four participants were on-study in Cohort 5 during the COVID-19 pause. One participant had completed the specified 24-week follow-up and was off study before the pause. All participants had reached Day 28 and initiated ART by the end of February 2020.
- **IMPACT: MODERATE**
 - There is no impact to the primary efficacy outcome (i.e., all participants had reached Day 28 before the COVID-19 pause) nor to any secondary outcome involving HIV-1 RNA.
 - The primary PK endpoint has the potential to be affected as some Week 12 visits were conducted virtually (and thus no labs were collected). The A5377 team pharmacologist will make the appropriate accommodations in the calculation of the PK parameters and document them in the PK analysis plan.
 - Analysis windows have been widened to capture as much information as possible. The Week 24 visit window will be further expanded to capture in-person visits for all participants.
 - Note: Per Protocol Version 3.0 this Cohort 5 will be closed (although it did not enroll 6 participants).

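### The per-cohort Wilcoxon tests kept in the primary Arm B analysis cannot reach an exact two-sided 0.05 at the enrolled sizes of 5 and 2, and no enrolled cohort has the N = 6 behind the 80% power

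*SAP*

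**What the plan says.** The primary efficacy outcome is the Day 7 change in log10 plasma HIV-1 RNA in Arm B. Section 4.2.1 of the SAP analyses it by a paired t-test with a two-sided 95% confidence interval for the cohorts combined, "and a Wilcoxon signed rank test for each cohort separately". It adds a combined signed-rank test as a sensitivity analysis. Section 4.2.2 extends this: "Similar analyses described in section 4.2.1 for the primary efficacy endpoint at Day 7 will be conducted for the Day 14 results". Neither section gives a sidedness, a significance level, or a choice between exact and asymptotic p-values for the per-cohort test.

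Section 2.5 states: "For the primary outcome measure of efficacy in Arm B, the study has 80% power to detect a drop of" 1.7 log10 copies/mL in each cohort with N = 6.

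On enrolment, the SAP reports:

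- **Cohort 5:** "Four participants were on-study in Cohort 5 during the COVID-19 pause", and one more had already finished and left the study (6.1). The same section says "this Cohort 5 will be closed (although it did not enroll 6 participants").
- **Cohort 7:** "Cohort 7 never opened to enrollment" (2.2).
- **Cohort 8:** section 4.2.2 cites "the limited sample size in Cohort 8 (n=2"), and section 2.2 says nobody was added under Protocol Version 4.0.

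Version 4.0 of the SAP did adapt other Arm B analyses. For the primary PK outcome, "For arm B participants, only descriptive statistics will be provided" (4.2.1), and viral decay modelling was dropped (4.2.2).

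**The concern.** A signed-rank test on a handful of participants has a smallest possible p-value fixed by the sample size alone. If that floor lies above the significance level, the test cannot reject whatever the treatment does. The per-cohort tests belong to the primary efficacy analysis, and under section 1.1 those results go into the primary manuscript and onto ClinicalTrials.gov. Hypothesis 3 in section 2.3 concerns dose-dependent activity, so readers will look at the results cohort by cohort. A reader who sees p > 0.05 for a cohort, beside a statement of 80% power per cohort, could take it as evidence of no activity at that dose. Under the exact two-sided reading, no data could have given any other result.

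**Working it through.** **Inputs.**

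- Cohort 5: 4 + 1 = 5 (SAP 6.1). The total is inferred, but the cohort did not reach 6, so 5 is also the maximum.
- Cohort 7: 0 (SAP 2.2). Cohort 8: 2 (SAP 4.2.2).
- Combined: 5 + 2 = 7.
- The efficacy population (SAP 4.1.1) requires entry HIV-1 RNA of at least 5000 copies/mL, which can only lower these numbers. The Safety-population sensitivity analysis cannot raise them above the numbers enrolled.
- Level: two-sided 0.05 is an assumption. The two-sided 95% interval for the combined analysis is the only level in the efficacy section.

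**The stated 80%.** It can be neither reproduced nor refuted, because the supplied text gives no SD, significance level or test for it. Working backwards from a drop of 1.7 and N = 6, an exact two-sided signed-rank test at 0.05 rejects only if all six changes share a sign. Power is then about Φ(1.7/SD)^6, which equals 0.80 at SD ≈ 0.95. A two-sided paired t-test gives 80% at SD ≈ 1.19. Both are possible, so the figure is not shown to be wrong.

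**Smallest attainable p-value.** Take the most extreme outcome: all n changes in one direction, with no ties or zeros.

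- Exact: two-sided p = 2/2^n; one-sided p = 1/2^n.
- Normal approximation: z = [n(n+1)/4] / √[n(n+1)(2n+1)/24]. For n = 5, z = 7.5/√13.75 = 2.023. For n = 4, z = 5/√7.5 = 1.826. For n = 2, z = 1.5/√1.25 = 1.342. The continuity correction subtracts 0.5 from the numerator.

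| n | Exact two-sided | Exact one-sided | Normal two-sided, uncorrected | Normal two-sided, corrected | Normal one-sided, uncorrected |
|---|---|---|---|---|---|
| 2 (Cohort 8) | 0.50 | 0.25 | 0.180 | 0.371 | 0.090 |
| 4 (Cohort 5 less one) | 0.125 | 0.0625 | 0.068 | 0.100 | 0.034 |
| 5 (Cohort 5) | 0.0625 | 0.031 | 0.043 | 0.059 | 0.022 |
| 6 (planned; or combined less one) | 0.031 | 0.016 | 0.028 | 0.036 | 0.014 |
| 7 (combined) | 0.0156 | 0.008 | 0.018 | 0.022 | 0.009 |

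The smallest n with an exact two-sided p below 0.05 is 6, the planned cohort size.

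**Power at the enrolled sizes.** With the exact two-sided test at 0.05 and a true drop of 1.7, power at n = 6 runs from 99.8% (SD 0.5) to 62% (SD 1.19). At n = 5 and n = 2 it is 0% for every SD, because the floor exceeds 0.05.

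**The case against.** The strongest reply is that the 0.05 threshold is the reader's, not the SAP's. Section 4.2.1 sets no level or decision rule for the per-cohort test, dose de-escalation uses responder counts (2.6.1), and the study has closed. For Cohort 5 the answer turns on a choice that section 1.1 may leave to the Analysis Implementation Plan, which was not supplied: a one-sided test or an uncorrected normal approximation could go below 0.05 at n = 5. This stands as a limit on the claim for Cohort 5, not for Cohort 8. It also argues for fixing the choice in the SAP, since section 4.2.2 shows that Cohort 5 results were already known.

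Second, the 80% is explicitly conditional on N = 6, and the shortfall is disclosed elsewhere in the SAP. That is true, so the point is an unmet condition left unmarked in 2.5, not a calculation error.

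Third, the SAP already provides per-cohort summaries and individual plots, and at n = 5 the p-value still separates 0.0625 from larger values. Both are fair. The problem lies in a significant/non-significant reading, not in the display of the data.

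Fourth, relabelling a planned test after seeing data is itself a data-aware change. That is a real cost and should be recorded.

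Finally, the combined signed-rank sensitivity test is safe only while n is at least 6. Two exclusions under the 5000 copies/mL rule would leave n = 5 and the same 0.0625 floor. This is correct, but the combined primary test is a paired t-test, which has no such floor.

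**Conclusion.** The concern holds and should be fixed. Assuming an exact two-sided test at 0.05 and at most 5 participants in Cohort 5, neither per-cohort test can be significant: the floors are 0.0625 in Cohort 5 (0.125 if one participant is excluded) and 0.50 in Cohort 8. For Cohort 8 the conclusion needs no assumption about sidedness or approximation; for Cohort 5 it does. The enrolled sizes of 5, 0 and 2 leave no cohort to which the 80% applies. The defect is confined to the per-cohort tests at Day 7 and Day 14 and to the unqualified power statement. The combined paired t-test is not affected.

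**What to change.** In section 2.5, add:

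> The 80% figure is the design value at N = 6. No Arm B cohort reached N = 6 (Cohort 5: 5; Cohort 7: 0; Cohort 8: 2). At these sizes an exact two-sided signed-rank test within a cohort cannot reach 0.05.

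In section 4.2.1, and for Day 14 in section 4.2.2, replace the per-cohort test with:

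> Per-cohort results are descriptive: each participant's change, with the cohort median and range. Any per-cohort signed-rank p-value is exact, two-sided and non-inferential. Inference rests on the combined analysis.

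Give the number analysed beside every p-value, and note that the combined signed-rank sensitivity test meets the same floor if fewer than 6 participants qualify. Record in section 1.2 that the change was made after Arm B data were seen.

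This costs wording only, with no new data or participants. The price is a less favourable power statement and a planned p-value relabelled after the fact. The remaining inference rests on a combined group in which 5 of 7 come from the 1 mg/kg cohort, so it cannot separate doses.

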4.2.2 Analysis of Secondary Outcomes

- **Plasma HIV-1 RNA (\log_{10} copies/mL) at baseline and post-infusion for treatment-naïve, viremic participants with HIV (Arm B cohorts)**

Longitudinal participant-specific plots for antiviral activity before initiation of ART will be presented for each participant in Arm B. **Given the little evidence of viral decay in Cohort 5 and the limited sample size in Cohort 8 (n=2), the planned modelling for viral decay will not be conducted.**

- **Change in plasma HIV-1 RNA (\log_{10} copies/mL) from baseline (defined as the last measurement taken prior to treatment initiation) to Day 7 and Day 14 of monotherapy, and maximum reduction during 14 days of monotherapy for treatment-naïve, viremic participants with HIV (Arm B cohorts)**

Similar analyses described in section 4.2.1 for the primary efficacy endpoint at Day 7 will be conducted for the Day 14 results. Summary statistics will be provided for the maximum reduction of each participant by dose cohort during monotherapy of SAR441236 (post-infusion and before ART initiation). **Protocol Version 4.0 considers the maximum reduction during 14 days of monotherapy because the timing for ART initiation/re-initiation was changed from “by 28 days” (Version 3.0 or earlier) to “at 14 days” for Arm B participants. However, since no participants enrolled under Version 4.0, we consider maximum reduction occurring in up to 28 days of monotherapy for Arm B participants.**

- **Attributions of anti-SAR441236 antibodies in all cohorts.**

The ADA status of participants exposed to anti-SAR441236 antibodies will be tabulated by scheduled visit day/week. Details of participants who developed anti-SAR441236 antibodies will be provided.

- **Change in CD4⁺ T-cell counts (cells/mm³) from baseline to week 12 following single dose of SAR441236 for all cohorts and the change in CD4⁺ T-cell counts (cells/mm³) from baseline to week 12 following each infusion for Cohort 4.**

Longitudinal participant-specific plots and numerical summaries for change from baseline in CD4⁺ T-cell counts (cells/mm³) will be presented by cohort.

- **Pharmacokinetic parameters of SAR441236 following each infusion.**

Descriptive numerical summaries of the following PK parameters (protocol section 11.3) by dose cohort will be presented:

Single dose:

- Maximum concentration (C_{max})
- Time of maximum concentration (T_{max})
- Dose-normalized maximum concentration
- Terminal half-life
- Clearance (CL) for Arms A and B
- Apparent clearance (CL/F) for Arm C
- Volume of Distribution (V_d) for Arms A and B
- Apparent volume of distribution (V_d/F) for Arm C

Multi-Dose:

- Concentration 12-weeks after each infusion
- AUC AI (12 Week Post Dose 1 vs Dose 4)
- Trough AI (12 Week Post Dose 1 vs 4)
- AUC 12-24WK
- AUC 24-36 WK
- AUC 36-48 WK
- AUC 0 – 48 WK

These parameters, while different than those specified by the protocol, were calculated by the pharmacologist based on the available concentration data. Graphical approaches will display concentration curves over time. Please refer to the PK analysis plan for additional details on the estimation of these parameters.

- **Concentration (or dose)-response relationship between SAR441236 exposure and changes in plasma HIV-1 RNA from entry baseline to week 4 (or viral load nadir) (Arm B cohorts)**

Longitudinal participant-specific plots of SAR441236 concentration and HIV-1 RNA (log₁₀ copies/mL) over time will be presented. Additionally, AUC vs change in HIV-1 RNA will also be plotted. If able to be calculated, descriptive summaries of EC₈₀ and EC_{max} will be presented. Please refer to the PK analysis plan for additional details.

5 Report Contents

In addition to the tables, figures, and analysis results described above, the information in the following section will be included in the report. Additional details describing the presentation of this information can be found in the AIP.

